6.2.1.2. Supportive/Supplementary Analysis

Supportive Analyses

Missing Improvement in ISGA (binary variable) will be handled by using NRI in supportive analyses. Reporting results are the same as tables above for the main analysis.

Supplementary Analysis

An analysis using PPAS will be performed. It will use the same methodology and handling of intercurrent events as the main analysis.

6.2.2. Achievement of Success in ISGA at Day 29

6.2.2.1. Main Analysis

- Estimand strategy: Hypothetical.
- Analysis set: FAS. Participants with baseline ISGA score of Clear (0) or Almost Clear (1) will be excluded.
- Analysis methodology: The percentage of subjects achieving Success in ISGA at Day 29 will be compared between crisaborole arm and vehicle arm and the difference will be tested based on normal approximation to response rates.
- Intercurrent events and missing data: Data after treatment discontinuation prior to Day 29 will not be considered. Missing ISGA scores will be derived for the analysis using MI-MCMC.
- Reporting results:
 - Tables: The sample size, number, percentage and 95% CI of percentage of subjects achieving Success in ISGA at Day 29 will be presented for each treatment. Risk difference and the corresponding 95% CI and p-value for the test of difference based on normal approximation to response rates will also be presented at Day 29.

6.2.2.2. Supportive/Supplementary Analysis

Supportive Analyses

Missing Success in ISGA (binary variable) will be handled by using NRI in supportive analyses. Reporting results are the same as tables above for the main analysis.

Supplementary Analysis

An analysis using PPAS will be performed. It will use the same methodology and handling of intercurrent events as the main analysis.

6.2.3. Change from Baseline in Peak Pruritus NRS at Week 4 – for subjects ≥ 12 years

6.2.3.1. Main Analysis

- Estimand strategy: Hypothetical.
- Analysis set: FAS.
- Analysis methodology: change from baseline to Week 4 (Days 23-29) in weekly average of Peak Pruritus NRS for subjects ≥ 12 years, will be analyzed using a MMRM that includes treatment group, visit, and treatment group-by-visit interaction as factors and

baseline value as a covariate. Within-subject variability will be accounted for using a random effect with the first-order autoregressive (AR(1)) covariance matrix.

- Intercurrent events and missing data: Data after treatment discontinuation prior to Day 29 will not be considered. The weekly average is considered missing if Peak Pruritus NRS scores are missing for more than three days. If the scores are missing for less than four days, then the weekly average is computed as the mean of the scores for the non-missing days. Missing weekly average values will not be explicitly imputed and will be assumed to be MAR.
- Reporting results:
 - Tables: The sample size, LS mean of change from baseline and 95% CI for each treatment, LS mean of difference and the corresponding 95% CI, and p-value will be presented at Week 4.

6.2.3.2. Supplementary Analyses

An analysis using PPAAS will be performed. It will use the same methodology and handling of intercurrent events as the main analysis.

6.2.4. Success in ISGA and Improvement in ISGA over time

- Analysis set: FAS. Participants with baseline ISGA score of Clear (0) or Almost Clear (1) will be excluded for Success in ISGA.
- Analysis methodology: At Day 8, Day 15, Day 22 and Day 29, the percentage of subjects achieving Success or Improvement in ISGA will be compared between crisaborole arm and vehicle arm and the difference will be tested based on normal approximation to response rates.
- Missing data: Data after treatment discontinuation prior to Day 29 will not be considered. Missing data handling will be the same as in [Section 6.2.1.1](#).
- Reporting results:
 - Tables: The sample size, number, percentage and 95% CI of percentage of subjects achieving Success or Improvement in ISGA at Day 8, Day 15, Day 22 and Day 29 will be presented for each treatment. Risk difference and the corresponding 95% CI and p-values for the test of difference based on normal approximation to response rates will be presented.
 - Figures: For two treatments, line plots of the percentage of subjects achieving Success or Improvement in ISGA and 95% CIs at each post-baseline visit will be displayed graphically

6.2.5. Percent Change from baseline in EASI total score over time

- Analysis set: FAS.
- Analysis methodology: At Day 8, Day 15, Day 22 and Day 29, percent change from baseline in EASI total score will be analyzed using a MMRM that includes treatment group, visit, and treatment group-by-visit interaction as factors and baseline value as a covariate. Within-subject variability will be accounted for using a random effect with the first-order autoregressive (AR(1)) covariance matrix.
- Missing data: data after treatment discontinuation prior to Day 29 will not be considered. Missing data handling will be the same as in [Section 6.1.1.1](#).
- Reporting results:
 - Tables: The sample size, LS mean of percent change from baseline and 95% CI for each treatment, LS mean of difference and the corresponding 95% CI, and p-value will be presented for all post-baseline visits.
 - Figures: For two treatments, line plots of the LS means and 95% CIs at each post-baseline visit will be displayed graphically.

6.2.6. Change from baseline in %BSA over time

- Analysis set: FAS.
- Analysis methodology: At Day 8, Day 15, Day 22 and Day 29, change from baseline in %BSA with AD will be analyzed using a MMRM that includes treatment group, visit, and treatment group-by-visit interaction as factors and baseline value as a covariate. Within-subject variability will be accounted for using a random effect with the first-order autoregressive (AR(1)) covariance matrix.
- Missing values will not be explicitly imputed and will be assumed to be MAR.
- Reporting results:
 - Tables: The sample size, LS mean of change from baseline and 95% CI for each treatment, LS mean of difference and the corresponding 95% CI, and p-value will be presented for all post-baseline visits.

6.2.7. Achievement of EASI-50, EASI-75 over time

- Analysis set: FAS.
- Analysis methodology: At Day 8, Day 15, Day 22 and Day 29, the percentage of subjects achieving EASI-50 or EASI-75 will be compared between crisaborole arm and vehicle arm and the difference will be tested based on normal approximation to response rates.

- Missing data: Missing EASI scores will be derived for the analysis using MI-MCMC.
- Reporting results:
 - Tables: The sample size, number, percentage and 95% CI of percentage of subjects achieving EASI-50 or EASI-75 at Day 8, Day 15, Day 22 and Day 29 will be presented for each treatment. Risk difference and the corresponding 95% CI and p-values for the test of difference based on normal approximation to response rates will be presented.

6.2.8. Change from Baseline in Peak Pruritus NRS over time - for subjects ≥ 12 years

- Analysis set: FAS.
- Analysis methodology: change from baseline in weekly average of Peak Pruritus NRS at Week 1 (Days 2-8), Week 2 (Days 9-15), Week 3 (Days 16-22) and Week 4 (Days 23-29) for subjects ≥ 12 years, will be analyzed using a MMRM that includes treatment group, visit, and treatment group-by-visit interaction as factors and baseline value as a covariate. Within-subject variability will be accounted for using a random effect with the first-order autoregressive (AR(1)) covariance matrix.
- Missing data: Data after treatment discontinuation prior to Day 29 will not be considered. Missing data handling will be the same as in [Section 6.2.3.1](#).
- Reporting results:
 - Tables: The sample size, LS mean of change from baseline and 95% CI for each treatment, LS mean of difference and the corresponding 95% CI, and p-value will be presented at Week 1, Week 2, Week 3 and Week 4.
 - Figures: For two treatments, line plots of the LS means and 95% CIs at each week will be displayed graphically.

6.2.9. Change from Baseline in Patient Reported Itch Severity Scale over time - for subjects ≥ 6 years and < 12 years

- Analysis set: FAS.
- Analysis methodology: change from baseline in weekly average of Patient Reported Itch Severity Scale at Week 1, Week 2, Week 3 and Week 4, for subjects ≥ 6 years and < 12 years, will be analyzed using a MMRM that includes treatment group, visit, and treatment group-by-visit interaction as factors and baseline value as a covariate. Within-subject variability will be accounted for using a random effect with the first-order autoregressive (AR(1)) covariance matrix.
- Missing data: The weekly average is considered missing if Patient Reported Itch Severity Scales are missing for more than three days. If the scores are missing for less than four

days, then the weekly average is computed as the mean of the scores for the non-missing days. Missing weekly average values will not be explicitly imputed and will be assumed to be MAR.

- Reporting results:
 - Tables: The sample size, LS mean of change from baseline and 95% CI for each treatment, LS mean of difference and the corresponding 95% CI, and p-value will be presented for each week.

6.2.10. Change from Baseline in Observer Reported Itch Severity Scale over time - for subjects <6 years

- Analysis set: FAS.
- Analysis methodology: change from baseline in weekly average of Observer Reported Itch Severity Scale at Week 1, Week 2, Week 3 and Week 4, for subjects <6 years, will be analyzed using a MMRM that includes treatment group, visit, and treatment group-by-visit interaction as factors and baseline value as a covariate. Within-subject variability will be accounted for using a random effect with the first-order autoregressive (AR(1)) covariance matrix.
- Missing data: The weekly average is considered missing if Observer Reported Itch Severity Scales are missing for more than three days. If the scores are missing for less than four days, then the weekly average is computed as the mean of the scores for the non-missing days. Missing weekly average values will not be explicitly imputed and will be assumed to be MAR.
- Reporting results:
 - Tables: The sample size, LS mean of change from baseline and 95% CI for each treatment, LS mean of difference and the corresponding 95% CI, and p-value will be presented for each week.

6.2.11. DLQI, CDLQI, IDQOL, DFI, POEM, PGIS/OGIS, PGIC/OGIC over time

Endpoints:

- Change from baseline in DLQI total score for subjects aged 16 years and older at Day 15 and Day 29.
- Change from baseline in CDLQI total score for subjects aged 4-15 years at Day 15 and Day 29.
- Change from baseline in IDQOL total score for subjects aged 2-3 years at Day 15 and Day 29.

- Change from baseline in DFI total score for subjects aged 2-17 years at Day 15 and Day 29.
- Change from baseline in POEM total score for self-report subjects aged 12 years or older at Day 15 and Day 29.
- Change from baseline in POEM total score for proxy-report subjects ≥ 2 and < 12 years at Day 15 and Day 29.
- Change from baseline in weekly average of PGIS for subjects aged 12 years and older at Week 1, Week 2, Week 3 and Week 4.
- Change from baseline in weekly average of OGIS for subjects ≥ 2 and < 12 years at Week 1, Week 2, Week 3 and Week 4.
- Observed PGIC for subjects aged 12 years and older at Day 8, Day 15, Day 22 and Day 29.
- Observed OGIC for subjects ≥ 2 and < 12 years at Day 8, Day 15, Day 22 and Day 29.

Analysis:

- Analysis set: FAS
- Analysis methodology: Descriptive statistics will be summarized for the above endpoints.
- Missing data:

If two or more response options are checked, the response option with the highest score should be recorded. If there is a response between two boxes, the lower of the two score options should be recorded.

For DLQI, CDLQI, IDQOL, DFI and POEM, the total score is considered missing if more than one item is missing. If one item is missing then total score is computed as the simple algebraic sum of the final item scores for nine non-missing items.

For PGIS/OGIS, missing data for any day will not be imputed. The weekly average is considered missing if PGIS/OGIS scores are missing for more than three days. If the scores are missing for less than four days, then the weekly average is computed as the mean of the scores for the non-missing days.

For PGIC/OGIC, missing data will not be imputed.

- Reporting results:
 - Tables: For change from baseline in DLQI, CDLQI, IDQOL, DFI and POEM, the sample size, mean, standard deviation, median and range, will be presented for each

treatment at Day 15 and Day 29. For change from baseline in weekly average of PGIS and OGIS, the sample size, mean, standard deviation, median and range, will be presented for each treatment at Week 1, Week 2, Week 3 and Week 4. For observed PGIC and OGIC, the sample size, mean, standard deviation, median and range, will be presented for each treatment at Day 8, Day 15, Day 22 and Day 29.

CCI [REDACTED]

[REDACTED]

[REDACTED]

[REDACTED]

[REDACTED]

[REDACTED]

[REDACTED]

CCI [REDACTED]

[REDACTED]

[REDACTED]

[REDACTED]

[REDACTED]

[REDACTED]

CCI [REDACTED]

[REDACTED]

[REDACTED]

[REDACTED]

CCI [Redacted]

[Redacted]

[Redacted]

[Redacted]

[Redacted]

CCI [Redacted]

[Redacted]

[Redacted]

[Redacted]

[Redacted]

[Redacted]

CCI [Redacted]

[Redacted]

[Redacted]

[Redacted]

[Redacted]

[REDACTED]

[REDACTED]

[REDACTED]

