2. STUDY OBJECTIVES AND ENDPOINTS

Primary Objectives	Primary Endpoint(s)

 • To evaluate the efficacy of crisaborole ointment, 2% applied BID versus Vehicle in Chinese and Japanese pediatric and adult subjects (ages 2 years and older) with mild to moderate AD. • To evaluate the safety and tolerability of crisaborole ointment, 2% applied BID versus Vehicle in Chinese and Japanese pediatric and adult subjects (ages 2 years and older) with mild to moderate AD. 	
 • Efficacy endpoint: Percent Change from Baseline in Eczema Area and Severity Index (EASI) total score at Day 29. • Safety endpoint: TEAEs (including application site reactions) & SAEs and clinically significant changes in vital signs and clinical laboratory parameters.
Secondary Objectives	Secondary Endpoints

 • To evaluate the effect of crisaborole ointment, 2% applied BID versus Vehicle on additional efficacy endpoints in Chinese and Japanese pediatric and adults subjects (Ages 2 years and older) with mild to moderate AD. • To evaluate the effect of crisaborole ointment, 2% applied BID versus Vehicle on patient/observer reported outcomes over time in Chinese and Japanese pediatric and adults subjects (Ages 2 years and older) with mild to moderate AD. 	
 • Efficacy endpoints. 
 • Key secondary efficacy endpoints. 
 • Achievement of improvement in ISGA (defined as ISGA score of clear (0) or almost clear (1)) at Day 29. • Achievement of Success in ISGA (defined as an ISGA score of Clear (0) or Almost Clear (1) with at least a 2 grade improvement from Baseline) at Day 29. • Change from Baseline in Peak Pruritus Numeric Rating Scale (NRS) at Week 4 - for subjects ≥ 12 years. • Other secondary efficacy endpoints. 
 • Success in ISGA (defined as an ISGA score of Clear (0) or Almost Clear (1) with at least a 2 grade improvement from Baseline) over time. • Improvement in ISGA (defined as ISGA score of clear (0) or almost clear (1)) over time. • Percent Change from BL in EASI total score over time. • Change from Baseline in % BSA over time. • Achievement of EASI-50 ($\geq 50\%$ improvement from baseline) over time.

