9.2.3. Analysis of Other Secondary Endpoints

Other secondary efficacy endpoints including change from Baseline in % BSA, percent change from baseline in EASI total score at all time points other than Day 29, change from

baseline in weekly average of peak pruritus NRS of weeks other than Week 4, change from baseline in weekly average of Patient Reported Itch Severity Scale, and change from baseline in weekly average of Observer Reported Itch Severity Scale will be analyzed similarly as the primary efficacy endpoints using a linear mixed effect model for repeated measures.

Other secondary efficacy endpoints including EASI50 and EASI75 at all time points, as well as Success in ISGA and Improvement in ISGA at all time points other than Day 29, will be analyzed using normal approximation to response rates.

DLQI, CDLQI, IDQOL, DFI, POEM, PGIS/OGIS, PGIC/OGIC will be summarized descriptively, missing values will be handled following instrument-specific procedures when available and as per the SAP.

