
 To evaluate the effect of crisaborole ointment, 2% applied BID versus Vehicle on patient/observer reported outcomes over time in Chinese and 	
 Change from Baseline in Peak Pruritus Numeric Rating Scale (NRS) at Week 4 - for subjects ≥ 12 years. 	
The estimand is the hypothetical estimand, which estimates the effect if all participants maintain their randomized treatment and adhere to the protocol. It includes the following 5 attributes:

Objectives	Endpoints	Estimands

Japanese pediatric and adult subjects (Ages 2 years and older) with mild to moderate AD.
		
 • Treatment: Crisaborole Ointment 2% BID vs Vehicle Ointment BID. • Population: Chinese and Japanese pediatric and adult subjects (ages 2 years and older) with mild to moderate AD as defined by the inclusion and exclusion criteria. • Variable: Change from Baseline in Peak Pruritus NRS at Week 4 for subjects ≥ 12 years. • Intercurrent events: Had patient not discontinued from treatment prior to Day 29. • Population-level summary: Difference in means between crisaborole ointment 2% BID vs corresponding vehicle.

Other Secondary:
	
Other Secondary:
	
Other Secondary:

 • To evaluate the effect of crisaborole ointment, 2% applied BID versus Vehicle on additional efficacy endpoints in Chinese and Japanese pediatric and adult subjects (Ages 2 years and older) with mild to moderate AD. • To evaluate the effect of crisaborole ointment, 2% applied BID versus Vehicle on patient/observer reported outcomes over time in 	
 • Success in ISGA (defined as an ISGA score of Clear (0) or Almost Clear (1) with at least a 2 grade improvement from Baseline) over time. • Improvement in ISGA (defined as ISGA score of clear (0) or almost clear (1)) over time. • Percent change from Baseline in EASI total score over time. • Change from Baseline in % body surface area (BSA) over time. • Achievement of EASI-50 ($\geq 50\%$ improvement from baseline) over time. • Achievement of EASI-75 ($\geq 75\%$ improvement from baseline) over time. • Change from baseline in Peak Pruritus NRS over time - for subjects ≥ 12 years. 	
No estimands will be defined.

Objectives	Endpoints	Estimands

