3.2. Secondary Endpoints

Efficacy endpoints:

- Key secondary efficacy endpoints
 - Achievement of Improvement in ISGA (defined as ISGA score of clear (0) or almost clear (1)) at Day 29.

- Achievement of Success in ISGA (defined as an ISGA score of Clear (0) or Almost Clear (1) with at least a 2 grade improvement from Baseline) at Day 29.
- Change from Baseline in Peak Pruritus Numeric Rating Scale (NRS) at Week 4 - for subjects ≥ 12 years.
- Other secondary efficacy endpoints
 - Success in ISGA (defined as an ISGA score of Clear (0) or Almost Clear (1) with at least a 2 grade improvement from Baseline) over time.
 - Improvement in ISGA (defined as ISGA score of clear (0) or almost clear (1)) over time.
 - Percent change from Baseline in EASI total score over time.
 - Change from Baseline in %BSA over time.
 - Achievement of EASI-50 ($\geq 50\%$ improvement from baseline) over time.
 - Achievement of EASI-75 ($\geq 75\%$ improvement from baseline) over time.
 - Change from baseline in Peak Pruritus NRS over time - for subjects ≥ 12 years.
 - Changes from baseline in Patient Reported Itch Severity Scale over time - for subjects ≥ 6 years and < 12 years.
 - Change from baseline in Observer Reported Itch Severity Scale over time - for subjects < 6 years.
 - DLQI, CDLQI, IDQOL, DFI, POEM, PGIS/OGIS, PGIC/OGIC over time.

CCI [REDACTED]

- [REDACTED]
- [REDACTED]
- [REDACTED]
- [REDACTED]

[REDACTED]

[REDACTED]

[REDACTED]

[REDACTED]

[REDACTED]

[REDACTED]

[REDACTED]

[REDACTED]

[REDACTED]

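### Seven patient/observer-reported instrument families get per-arm descriptive statistics only, although the secondary objective they serve is the effect versus vehicle; a between-arm difference with 95% CI would be a cheap addition

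*SAP*

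**What the plan says.** Protocol Section 2 sets this secondary objective: "To evaluate the effect of crisaborole ointment, 2% applied BID versus Vehicle on patient/observer reported outcomes over time". SAP 2.1 repeats it. SAP 3.2 lists "DLQI, CDLQI, IDQOL, DFI, POEM, PGIS/OGIS, PGIC/OGIC over time" among the other secondary efficacy endpoints, next to the itch scales.

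The analysis of these instruments is descriptive wherever it is described:

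- Protocol 9.2.3: "DLQI, CDLQI, IDQOL, DFI, POEM, PGIS/OGIS, PGIC/OGIC will be summarized descriptively".
- Protocol 7.1.6.5: the quality-of-life scores are summarised descriptively by treatment group.
- SAP 6.2.11: "Analysis methodology: Descriptive statistics will be summarized for the above endpoints". The change scores for DLQI, CDLQI, IDQOL, DFI and POEM are summarised per arm by n, mean, SD, median and range at Days 15 and 29. Weekly averages of PGIS and OGIS are treated likewise at Weeks 1 to 4. Then: "For observed PGIC and OGIC, the sample size, mean, standard deviation, median and range, will be presented for each treatment at Day 8", and likewise at Days 15, 22 and 29.
- SAP Appendix 1: the method column for this row reads as descriptive statistics.

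The itch scales are handled differently. SAP 6.2.3 and 6.2.8 to 6.2.10 fit a repeated-measures model with baseline as covariate and report the least-squares mean difference with its 95% CI and a p-value.

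**The concern.** The objective is comparative, but the planned output for seven instrument families stops at each arm separately. Anyone asking how large the effect on quality of life or POEM is must subtract two raw mean changes.

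That subtraction lacks two things the SAP provides for its other continuous efficacy endpoints. The first is baseline adjustment, which improves precision and accounts for chance imbalance. The second is the use of earlier visits, under a missing-at-random assumption, for subjects who miss a later one. SAP 5.3 says that descriptive statistics in general use no imputation, and SAP 6.2.11 does not impute missing total scores or weekly averages. The planned means are therefore observed-case. If dropout depends on earlier response or differs by arm, their difference can be biased.

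**Working it through.** The plan states no figure on this point. The check is a comparison of text, followed by a calculation of what could be estimated.

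**1. Is there a visible reason for the split between the itch scales and the other instruments?**

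- *Data structure.* PGIS/OGIS are collected daily, averaged over the same weekly windows as the pruritus NRS (SAP Appendix 2.1, Table 5), and set to missing under the same rule (more than three days missing). The NRS is modelled; PGIS/OGIS are not.
- *Sample size.* SAP 2.2 plans about 384 subjects, half aged 12 or over, so about 192 in each age group. Self-report POEM and PGIS cover the same 192 or so as the Peak Pruritus NRS. Proxy POEM and OGIS cover the other 192 or so. The two paediatric itch scales (6 to under 12, and under 6) divide that second group, so at least one has about 192/2 = 96 subjects or fewer. Both are modelled.
- *Baseline.* SAP 3.4 lists baseline values for all the instruments except PGIC/OGIC, which rate change and have no baseline.
- *General method.* SAP 5.2.2 makes the repeated-measures model the general method for continuous endpoints without explicit imputation. SAP 6.2.11 neither calls on it nor says why not.

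**2. What precision is available?**

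Inputs: 2:1 allocation (both documents) and about 192 subjects aged 12 or over, giving 128:64. No missing data is assumed. The SD of POEM change is not in the documents; 5 to 7 points is an assumption.

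Half-width = 1.96 × SD × √(1/128 + 1/64) = 1.96 × SD × 0.1531 = 0.30 × SD

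| Assumed SD | Half-width (points) |
|---|---|
| 5 | 1.50 |
| 6 | 1.80 |
| 7 | 2.10 |

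The documents do not give the sizes of the age groups for DLQI, CDLQI, IDQOL and DFI. For assumed totals of 96, 60 and 40 at 2:1, the same formula gives 0.42, 0.54 and 0.66 SD.

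**3. What does baseline adjustment add?**

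Take equal variance σ² at baseline and follow-up, with correlation r. A change score has variance 2σ²(1 − r); a baseline-adjusted outcome has residual variance σ²(1 − r²). The ratio of standard errors is √((1 + r)/2).

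| r | SE ratio | Reduction in SE |
|---|---|---|
| 0.3 | 0.81 | 19% |
| 0.5 | 0.87 | 13% |
| 0.7 | 0.92 | 8% |

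**4. How much output would be added?**

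Six scores (DLQI, CDLQI, IDQOL, DFI, self-report POEM, proxy POEM) × 2 visits = 12. PGIS and OGIS × 4 weeks = 8. PGIC and OGIC × 4 visits = 8. The total is 28 intervals.

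**The case against.** A good case can be made for leaving the plan as it is.

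- **The plan is consistent and tiered.** Both documents say descriptive throughout, and Protocol 9.2.3 separates the modelled itch scales from these instruments. They lie outside the testing sequence in SAP 5.1, and SAP 2.1 defines no estimands at this level. Descriptive reporting of such endpoints is a legitimate choice. This stands, and it limits how much weight the point can bear.
- **The objective is partly served.** It concerns reported outcomes as a class. The three itch scales between them cover every age from 2 years up, and all get a difference with a CI. This also stands; the gap concerns the other seven families only.
- **Some instruments have another role.** Protocol 7.1.6.2 and 7.1.6.3 describe PGIS/OGIS and PGIC/OGIC as anchors for interpreting the itch scales. That makes a descriptive summary less surprising, but they are still listed as endpoints under the comparative objective.
- **More intervals invite informal testing.** Twenty-eight intervals without multiplicity control could be read as significance tests. This is a real cost, which labelling reduces but does not remove.

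A reader might infer that the objective cannot be answered at all for these instruments, or only without any measure of precision. The documents do not support that: n, mean and SD per arm are enough to derive a crude difference and CI. Nor do they support a claim that the unadjusted change is biased by baseline imbalance. It is unbiased over randomisation, and baseline values will be tabulated. Redacted text follows SAP 6.2.11, so the point is limited to the visible plan and the redaction is not counted as a gap.

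**Conclusion.** The point holds as a gap between a comparative objective and a descriptive analysis for seven instrument families. What is missing is a planned between-arm estimate with its CI and, where the instrument has a baseline, baseline adjustment and missing-at-random handling of missed visits.

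It is not a contradiction between the documents, and it does not touch the primary or key secondary conclusions. It should be made as an inexpensive improvement to lower-tier endpoints.

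The POEM figures show that a usable estimate is feasible in one of the larger groups. They rest on an assumed SD, 128:64 allocation and no missing data. The 8% to 19% reduction in standard error rests on equal baseline and follow-up variances and r between 0.7 and 0.3. Neither calculation shows that any conclusion would change.

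**What to change.** In SAP 6.2.11, add:

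- for DLQI, CDLQI, IDQOL, DFI and POEM, the baseline-adjusted treatment difference with 95% CI at Days 15 and 29, from the SAP 5.2.2 repeated-measures model;
- for PGIS and OGIS, the same at Weeks 1 to 4;
- for PGIC and OGIC, the difference in mean score with 95% CI at each visit.

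Report no p-values, as SAP 6.4 already does for its subgroup analyses, and label the intervals as not multiplicity-controlled. The testing sequence in SAP 5.1 is unaffected. Align Protocol 9.2.3, Protocol 7.1.6.5 and SAP Appendix 1.

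The cost is SAP and protocol wording and some additional model runs on data already being collected. The downsides are more tables, intervals that may be read as tests, and wide intervals in small age groups such as the IDQOL group (ages 2 to 3).

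A cheaper alternative is to reword the objective as descriptive for these instruments. That would also close the gap, but would leave the collected comparative information unused.
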